5 STUDY POPULATION

Prospective approval of protocol deviations to recruitment and enrollment criteria, also known as protocol waivers or exemptions, is not permitted.

5.1 INCLUSION CRITERIA

Participants are eligible to be included in the study only if all of the following criteria apply:

Age

I 01. Participant must be ≥ 18 years of age at the time of signing the informed consent.

Type of participant and disease characteristics

I 02. Participants with T2DM and HbA1c $> 7\%$

I 03. Participants who meet at least one of the 9 CVD criteria in [Table 3](#)

OR

male participants who are ≥ 50 years of age or female participants who are ≥ 55 years of age and have an eGFR ≥ 25 and < 60 mL/min and have at least one of the 6 CV risk factors listed in [Table 4](#)

Table 3 - Established CVD criteria (need at least 1 from Section A, B or C)

Section A: Presence of Coronary Artery Disease (CAD)

1. Documented (with ECG changes or prior discharge hospital diagnosis) history of symptomatic myocardial infarction (> 2 months prior to screening)
2. Evidence of multi-vessel coronary artery disease, ie, ≥ 2 major coronary arteries or the left main coronary artery, documented by any of the following:
 - Presence of a significant stenosis (imaging evidence of $\geq 50\%$ narrowing of the luminal diameter measured during a coronary angiography or a multi-sliced computed tomography)
 - Previous revascularization of ≥ 2 major coronary arteries (percutaneous transluminal coronary angioplasty (with or without stent), or CABG) (> 2 months prior to screening)
 - The combination of revascularization in one major coronary artery (> 2 months prior to screening) and the presence of a significant stenosis in another major coronary artery ($\geq 50\%$ luminal narrowing during an angiography (coronary or multi-sliced computed tomography))
3. Evidence of single vessel coronary artery disease of at least $\geq 50\%$ luminal narrowing during a angiography (coronary or multi-sliced computed tomography) not subsequently successfully revascularized, with at least 1 of the following:
 - A positive non-invasive stress test for ischemia
 - Hospitalization for unstable angina within the prior 12 months

Section B: Presence of Cerebrovascular Disease

4. History of Ischemic or Haemorrhagic stroke (> 2 months prior to screening)
-

Section C: Presence of Peripheral Arterial Disease (PAD) (symptomatic or not)

5. Previous limb angioplasty
 6. Stenting or bypass surgery of peripheral artery
 7. Previous limb or foot amputation due to circulatory insufficiency
 8. Ankle-brachial index <0.9
 9. Angiographic evidence of PAD
-

CABG: coronary artery bypass graft; ECG: electrocardiogram

Table 4 - CV Risk Factors (at least 1 criterion must be met)

-
1. Body mass index ≥ 35 kg/m² at Screening
 2. Dyslipidemia despite maximally-tolerated statin therapy:
 - Based on the last measured and documented laboratory measurement in the previous 6 months
 - LDL cholesterol >130 mg/dL (>3.36 mmol/L)
 - OR
 - HDL cholesterol <40 mg/dL (<1.03 mmol/L) for men or <50 mg/dL (<1.29 mmol/L) for women
 3. Currently smoking tobacco (Consumes an average of at least 1 cigarette, pipe, or cigar per day, at Screening)
 4. UACR ≥ 30 mg/g (3 mg/mmol) during Screening period, based on central laboratory (spot urine)
 5. SBP >140 mmHg and DBP >90 mmHg despite antihypertensive therapy at the Screening Visit
 6. Family history (in a male relative <55 years or in a female relative <65 years) of premature coronary heart disease (defined as MI or coronary revascularization procedure) in a first degree relative.
-

DBP: diastolic blood pressure; HDL: high density lipoprotein; LDL: low density lipoprotein; SBP: systolic blood pressure; UACR: urinary albumin-creatinine ratio

Sex

I 04. Male or Female

A female participant is eligible to participate if she is not pregnant (see Appendix 4 [Section 10.4]), not breastfeeding, and at least one of the following conditions applies:

- Not a WOCBP as defined in Appendix 4 (Section 10.4)

OR

- A WOCBP who agrees to follow the contraceptive guidance in Appendix 4 (Section 10.4) during the study and for at least 5 weeks after the last dose of study treatment and who agrees to refrain from donating ova for the duration of the study and at least 5 weeks after last dose of study treatment.

Informed Consent

- I 05. Capable of giving signed informed consent as described in Appendix 1 ([Section 10.1.2](#)) which includes compliance with the requirements and restrictions listed in the informed consent form (ICF) and in this protocol.

5.2 EXCLUSION CRITERIA

Participants are excluded from the study if any of the following criteria apply:

Medical conditions

- E 01. Clinically relevant history of GI disease associated with prolonged nausea and vomiting, including (but not limited to) gastroparesis, unstable and uncontrolled gastroesophageal reflux disease within 6 months prior to screening
- E 02. History of pancreatitis (unless pancreatitis was related to gallstone and cholecystectomy has been performed) and pancreatitis during previous treatment with incretin therapies, chronic pancreatitis, and pancreatectomy
- E 03. Personal or family history of medullary thyroid cancer (MTC) or genetic conditions that predisposes to MTC (eg, multiple endocrine neoplasia syndromes)
- E 04. Estimated glomerular filtration rate <25 mL/min/1.73 m² by the 4 variable Modification of Diet in Renal Disease (MDRD) equation (at Screening, based on central laboratory)
- E 05. Systolic BP >180 mmHg and/or DBP >100 mmHg at randomization
- E 06. Hospitalization for hypertensive emergency within 3 months prior to randomization
- E 07. Planned coronary revascularization procedures, electrophysiologic device implantation, cardiac mechanical support implantation or other cardiac surgery
- E 08. History of solid organ transplant
- E 09. Hypersensitivity to any of the study treatments, any components thereof, or any GLP-1 RAs (eg, exenatide, liraglutide, lixisenatide, albiglutide, dulaglutide, semaglutide)
- E 10. No documented ophthalmologic exam with fundoscopy within 6 months prior to randomization (or within 3 months in patients with severe non proliferative diabetic retinopathy [NPDR]/ proliferative diabetic retinopathy [PDR]/Diabetic Macular Edema [DME])
- E 11. Retinopathy or maculopathy with one of the following treatments, either recent (3 months prior to randomization) or planned during the study: intravitreal injections or laser or vitrectomy surgery

- E 12. Patients with short life expectancy or with any clinically significant abnormality identified in their medical history (including severe anemia, congestive heart failure-New York Heart Association [NYHA] III/IV, respiratory, hepatic, neurological, psychiatric, active malignant tumor or other major systemic disease), during screening evaluation (eg, physical examination, laboratory tests, ECG, vital signs), or due to any AE during the screening period, which, in the judgement of the investigator, would preclude safe participation in the study or constrain efficacy assessment
- E 13. History of drug or alcohol abuse within 6 months prior to the time of screening

Prior/concomitant therapy

- E 14. Treated with any GLP-1 RA product alone (eg, exenatide, liraglutide, lixisenatide, albiglutide, dulaglutide, semaglutide) or in combination, within 3 months prior to screening
- E 15. Use of any DPP4 inhibitor within 3 months prior to screening
- E 16. Diabetic treatment has not been stable in the 3 months prior to screening, in the opinion of the investigator

Prior/concurrent clinical study experience

- E 17. Exposure to any investigational drugs in the last 4 weeks or 5 half-lives, whichever is longer, prior to screening
- E 18. Current enrollment in any other clinical study involving an investigational study treatment
- E 19. Participation in any previous efpeglenatide/HM11260C clinical trial within 3 months prior to screening

Diagnostic assessments

- E 20. Laboratory findings at the Screening Visit:
- ALT or AST >3 times the ULN
 - Total bilirubin >1.5 times the ULN (except in case of documented Gilbert's syndrome)
 - Amylase and/or lipase >3 times the ULN laboratory range
 - Calcitonin \geq 5.9 pmol/L (20 pg/mL)

Other exclusions

- E 21. Presence of any other conditions (eg, geographic, social) actual or anticipated, that the Investigator feels would restrict or limit the patient's participation for the duration of the study

- E 22. Participant is an employee of the Sponsor, or is the Investigator or any Subinvestigator, research assistant, pharmacist, study coordinator, other staff or relative thereof directly involved in the conduct of the protocol
- E 23. Participants unwilling or unable to comply with study procedures as outlined in the protocol
- E 24. Participants who withdraw consent during the Screening Period (starting from signed ICF)
- E 25. Any country-related specific regulation that would prevent the participant from entering the study (eg, individuals committed to an institution by virtue of an order issued either by the judicial or the administrative authorities) – see Appendix 8 ([Section 10.8](#)) (country specific requirements)

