10.6.1 Monitoring of participants with increased lipase and/or amylase >2 ULN

GLP-1 RAs stimulate pancreatic beta-cell and suppress alpha-cell function. Some cases of acute pancreatitis have been reported with marketed GLP-1 RAs. Therefore participants enrolled in this study should be closely monitored for any suspected pancreatitis, eg, with symptoms and/or signs of acute abdominal distress or abnormal levels of pancreatic enzymes. Serum amylase and lipase concentrations are monitored routinely at Screening, Baseline and periodically during the study treatment period.

In the presence of clinical signs and/or symptoms evocative of pancreatitis, eg, persistent abdominal pain, which can radiate to the back, often with characteristic positional features, with possible occurrence of nausea, vomiting, fever and leucocytosis, further measurement of amylase and lipase should be performed. The clinical signs and/or symptoms should be documented in the source data.

10.6.2 Elevation of amylase and/or lipase >2 x ULN without clinical signs and/or symptoms

In any case where amylase and/or lipase are >2 x ULN, a retest (centrally assessed as far as possible) must be performed as follows:

- If value(s) is/are >2 to 3 x ULN: retest within 7 days,
- If value(s) is/are >3 x ULN: retest within 48 hours,
- If the value(s) remain(s) >2 x ULN upon retesting: amylase and/or lipase levels should be retested weekly until values are <2 x ULN.

In case a retest is >2 x ULN a gastroenterological evaluation and imaging (ultrasound and/or computed tomography [CT] or magnetic resonance imaging [MRI] with contrast, as appropriate) must be performed. The absence of clinical signs and/or symptoms should be documented in the source documents (if clinical signs and/or symptoms develop, please see [Section 10.6.3](#) below).

Best clinical judgment is to be used when interpreting elevated serum amylase and lipase levels in asymptomatic participants. Temporary discontinuation of the IMP may be considered in these cases if deemed necessary by the Investigator.

10.6.3 Elevation of amylase and/or lipase >2 x ULN with clinical signs and/or symptoms.

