In the presence of clinical signs and/or symptoms evocative of pancreatitis (as described above) associated with elevated amylase and/or lipase, treatment with the IMP should be promptly and at least temporarily discontinued pending further clinical evaluation and diagnosis confirmation. Clinical signs and/or symptoms are to be documented in the source data. A laboratory determination of amylase and lipase must be obtained at the time of the event and again within 48 hours or earlier as clinically indicated. If the value(s) remain(s) >2 x ULN, then amylase and/or

lipase levels should be retested as described in [Section 10.6.2](#) above, or more often if clinically indicated.

A gastroenterologic evaluation and imaging (ultrasound and/or CT or MRI with contrast, as appropriate) must be performed as clinically indicated and as per clinical practice and local guidelines. If a diagnosis of pancreatitis is confirmed, IMP should not be restarted and should be permanently discontinued. In both cases as described above under (1) and (2), all laboratory or clinical documentations are to be collected. If the retest confirms lipase and/or amylase values are >2 ULN, the event must be reported in the e-CRF on the AE form and the specific complementary forms, using the appropriate verbatim: eg, “increased amylase and/or lipase” in case of isolated enzyme elevation, “suspected pancreatitis” in the presence of clinical signs evocative of pancreatitis if the diagnosis is suspected but cannot be confirmed or excluded, and “pancreatitis” if the diagnosis has been confirmed.

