#### 2.1.4.1 Adverse events variables

##### *Adverse event classification*

The AE observations will be classified per the observation periods of safety data as defined above into:

- **Pre-treatment AEs** are adverse events that developed or worsened or became serious during the pre-treatment period
- **Treatment-emergent AEs (TEAEs)** are adverse events that developed or worsened or became serious during the on-treatment period
- **Post-treatment AEs** are adverse events that developed or worsened or became serious during the post-treatment period
- **On-study AEs** are adverse events that developed or worsened or became serious during the on-study period

All AEs (including SAEs), AEs of special interest (AESI) and AEs requiring specific monitoring (AERSM) will be coded to a lower-level term (LLT), preferred term (PT), high-level term (HLT), high-level group term (HLGT), and associated primary system organ class (SOC) using the version of MedDRA currently in effect at Sanofi at the time of database lock.

AESI include the following terms:

- Pregnancy of a female participant entered in a study as well as pregnancy occurring in a female partner of a male participant entered in a study with IMP
- Symptomatic overdose (serious or nonserious) with IMP
- alanine aminotransferase (ALT)  $\geq 3$  upper limit normal (ULN) (if baseline ALT <ULN) Or ALT  $\geq 2$  times the baseline value (if baseline ALT  $\geq$ ULN)

AERSM include the following terms:

- Severe gastrointestinal (GI) events
- Severe hypoglycemia
- Pancreatic events (including abnormal values of pancreatic enzymes, pancreatitis and pancreatic neoplasm)
- Calcitonin increase  $>5.9$  pmol/L (20 pg/mL) and thyroid C-cell neoplasm
- Acute renal failure
- Diabetic retinopathy complications
- Severe injection site reaction
- Severe allergic reactions
- Severe immune complex disease

The CEC will review pancreatic events in a blinded manner.

The criteria of AESI and AERSM are defined in below [Table 2](#).

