**Table 2 - Criteria for AESI and AERSM**

AE Grouping	Criteria
AESI	
Pregnancy	"Pregnancy" checked
Symptomatic Overdose	"Overdose" checked and symptomatic (AEOVSYMP) = "Yes"
ALT $\geq$ 3 ULN (if baseline ALT <ULN) Or ALT $\geq$ 2 times the baseline value (if baseline ALT $\geq$ ULN)	"ALT Increase" checked and Yes to the question "Is the event an AESI?" in eCRF form "Adverse Events"
AERSM	
Severe GI events	AE severity= "severe" using Gastrointestinal disorders CMQ
Severe hypoglycemia	Any hypoglycemia event which either required assistance (from hypoglycemia page) or missed answering 'Assistance Required' but with at least one of the 4 symptoms of one of the 4 symptoms (ie, coma, seizure, loss of consciousness, and confusion)
Pancreatic events	cases reported in pancreatic specific eCRF page or AE with category = "Pancreatic neoplasm" selected
Calcitonin and thyroid C-cell neoplasm	Using Calcitonin increase CMQ Using Medullary thyroid cancer CMQ
Acute renal failure	Using Acute renal failure Narrow CMQ
Diabetic retinopathy complications	AE category = "Diabetic Retinopathy"
Severe injection site reaction	Intensity = "Severe" + Using Injection site reaction_ CMQ
Severe allergic reactions	Intensity = "Severe" + CMQs for anaphylactic reaction, angioedema, severe cutaneous adverse reaction, anaphylactic/anaphylactoid shock conditions (under SMQ "Shock"), and hypersensitivity
Severe immune complex disease	Intensity = "Severe" using Immune complex disease CMQ

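### Amylase or lipase of >2 to 3 x ULN is admitted at entry but triggers work-up and reporting with no baseline term, so a stable elevation first reported after dosing can be counted as a treatment-emergent pancreatic event

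*Protocol*

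**What the plan says.** **Entry.** Protocol 5.2, E 20, excludes on screening "Amylase and/or lipase >3 times the ULN laboratory range". A value above 2 and up to 3 x ULN passes.

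**Work-up.** Protocol Appendix 6 (10.6.2), for participants without symptoms, opens with "In any case where amylase and/or lipase are >2 x ULN, a retest". If the value stays up, "amylase and/or lipase levels should be retested weekly until values are <2 x ULN". It adds "In case a retest is >2 x ULN a gastroenterological evaluation and imaging" as a mandatory step. Clinical judgment is invited for interpreting the values and for interrupting IMP. It does not waive the retest, the imaging or the report.

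**Reporting.** Under 10.6.3, once a retest confirms a value above 2 x ULN, "the event must be reported in the e-CRF on the AE form and the specific complementary forms".

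**Counting.** SAP 2.1.4.1 lists among the AERSM "Pancreatic events (including abnormal values of pancreatic enzymes, pancreatitis and pancreatic neoplasm". The matching row of SAP Table 2 starts "cases reported in pancreatic specific eCRF page or AE with category" and goes on to the pancreatic neoplasm category. Neither entry has a baseline condition. SAP 2.3.5.1 summarizes AERSM over the TEAE period, and SAP 2.1.4.1 defines a TEAE as an event that develops, worsens or becomes serious on treatment. Protocol Appendix 3 says that fluctuation of a condition present at study start, without worsening, is not an AE.

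**The concern.** Entry and action limits differ, and the action rules ignore the participant's own starting value. Someone who enters with a stable lipase of 2.5 x ULN meets the on-study trigger at the first post-dose sample without any change. The weekly retest rule gives that person no exit short of falling below 2 x ULN, and imaging follows from a value known at entry.

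For the analysis, the enzyme part of the pancreatic AERSM count can mix new elevations with ones that predate treatment. Appendix 6 gives reports of pancreatitis with marketed GLP-1 receptor agonists as the reason for monitoring these enzymes. A count padded equally in all arms pulls a relative comparison toward no difference. In a safety table, that error is on the reassuring side.

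**Working it through.** The plan states no figure on this point, so there is none to reproduce. The check compares the limits, follows one participant through the rules, and then sizes the effect under stated assumptions.

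**1. Limits side by side**

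| Marker | Excluded at entry (E 20) | On-study trigger | Baseline term |
|---|---|---|---|
| Amylase, lipase | >3 x ULN | >2 x ULN (Appendix 6) | None |
| ALT | >3 x ULN | ≥3 x ULN, or ≥2 x baseline if baseline is at or above ULN (Protocol 8.3) | Yes |
| Calcitonin | ≥20 pg/mL | ≥20 pg/mL (10.6.4) | Not needed; limits coincide |

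Of these three, only the pancreatic enzymes have neither aligned limits nor a baseline term.

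**2. One participant, lipase stable at 2.5 x ULN**

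- *Reported before dosing.* Enzymes are sampled at Screening and Week 0, and AEs are collected from consent (Protocol 8.3.1). If a site applies the retest rule during screening and files the report, onset is pre-treatment. Without worsening, the event stays out of the TEAE summary.
- *First reported after dosing.* If nothing is filed before the first dose, the Week 12 sample triggers a retest, the retest confirms, and reporting is mandatory. The record then carries an on-treatment onset. Table 2 takes it from the pancreatic page, and no step in the SAP compares it with baseline.
- *What the general AE rules say.* Appendix 3 points both ways. It excludes non-worsening fluctuation of a condition present at the start, but it includes conditions first detected after dosing even if they may have been present earlier. Incomplete onset dates default to treatment-emergent (SAP 2.3.5.1 and 2.5.3).

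Two sites could therefore classify identical participants differently.

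**3. Where else it would show**

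- Laboratory PCSA tables: SAP Appendix A sets lipase and amylase at ≥3 x ULN. A stable 2.5 x ULN is never a PCSA, and a baseline above 2 and below 3 x ULN sits in the normal/missing row. These tables are not inflated, but they do not reveal the group either.
- Dedicated pancreatic analysis (SAP 2.3.5.1): only positively adjudicated pancreatitis and pancreatic neoplasm. Not affected.

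**4. Illustrative size**

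Assumptions, none from the documents: a share p enters above 2 and up to 3 x ULN; true new-onset confirmed elevation is r per arm; every such entrant is confirmed on study and counted. The last makes this an upper bound for given p and r.

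Counted rate = p + (1 − p) × r. Participants = p × 4000.

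| p | Participants | Placebo, r = 2% | Efpeglenatide, r = 4% | Apparent RR | Difference |
|---|---|---|---|---|---|
| 0 | 0 | 2.00% | 4.00% | 2.00 | 2.00 points |
| 1% | 40 | 0.01 + 0.99 × 0.02 = 2.98% | 0.01 + 0.99 × 0.04 = 4.96% | 1.66 | 1.98 points |
| 3% | 120 | 4.94% | 6.88% | 1.39 | 1.94 points |
| 5% | 200 | 6.90% | 8.80% | 1.28 | 1.90 points |

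With r of 5% versus 10%, again a true RR of 2.0, the apparent RR is 1.83, 1.62 and 1.49.

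The difference barely moves, but its precision worsens. Take 4000/3 ≈ 1333 on placebo and 2667 on pooled efpeglenatide. The standard error at p = 0 is √(0.02 × 0.98/1333 + 0.04 × 0.96/2667) = 0.54 points. At p = 3% it is √(0.0494 × 0.9506/1333 + 0.0688 × 0.9312/2667) = 0.77 points.

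**The case against.** The strongest reply is that the documents contain no rule to count stable elevations. A reader might infer from Table 2 that every pre-existing elevation becomes an on-treatment pancreatic event. The text does not support that. AERSM are confined to the TEAE period, a TEAE must develop or worsen, and Appendix 3 excludes non-worsening pre-existing conditions. Appendix 6 also lacks the carve-out for screening that the ALT algorithm in Appendix 5 has, so a literal reading could put the first report before treatment. This stands: miscounting is a possibility created by a mandatory first report after dosing.

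Second, the adjudicated pancreatic analysis is untouched, safety analyses are descriptive without hypothesis tests, and background cases are balanced in expectation under randomization and blinding. This also stands and limits the stakes.

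Third, part of the remedy exists. Appendix 6 prescribes different verbatim terms for isolated enzyme rises, suspected pancreatitis and confirmed pancreatitis. AERSM are tabulated by preferred term, and laboratory values are summarized as change from baseline. This stands in part: enzyme-only events can be told apart from clinical ones, but nothing separates new elevations from old ones within the enzyme-only count.

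Fourth, a lower on-study trigger may be deliberate caution. That is a clinical choice on which this point takes no position. It does not explain why the counting rule has no baseline reference.

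**Conclusion.** The point holds as an internal inconsistency with a limited analytic consequence. Participants admitted above 2 and up to 3 x ULN can be worked up repeatedly for a value they entered with. If they are first reported after dosing, they can enter the treatment-emergent pancreatic AERSM count against the SAP's TEAE definition and the non-worsening exclusion in Appendix 3.

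The effect is confined to the descriptive enzyme-related AE and AERSM counts. It is dilution and noise, with no expected direction between arms. Its size cannot be stated from the documents; the apparent relative risks of 1.66 to 1.28 rest wholly on assumed prevalence and onset rates and on every such entrant being counted. Neither the adjudicated pancreatitis and neoplasm summary nor the primary endpoint is affected. The change is worth making because it is cheap.

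**What to change.** **SAP, before unblinding.** In Table 2 and 2.3.5.1, derive a flag for enzyme-only pancreatic events from the central-laboratory amylase and lipase already collected. Treat such an event as treatment-emergent only if the confirmed value is a worsening from the participant's own baseline, as defined in SAP 2.1.1. The ALT criterion is a model for the structure. Tabulate these events by baseline ≤2 versus >2 x ULN, separately from clinical pancreatic events. State what happens when a confirming retest was done locally, since Appendix 6 asks for central retesting only as far as possible.

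**Protocol.** Reconcile E 20, the AE definition in Appendix 3 and the Appendix 6 retest, imaging and reporting rules with each other and with the SAP's AERSM criteria. Say whether the Appendix 6 rules apply during screening. Which enzyme limits and work-up rules apply is for the sponsor to decide.

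**Cost.** A few sentences, one derived flag and one extra table split, with no new data. Flagged counts will be lower than the number of forms filed, so the unflagged count should be shown beside them.
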